### 11.6. Laboratory data

Local and central laboratory assessments will be collected in the eCRF.

### 11.6.1. Laboratory variables

Laboratory parameters measured in the central laboratory can be classified into

- Blood parameters from
  - Haematology
  - Serum biochemistry
  - Coagulation parameters
  - Serology parameters for HBV (HBsAg, HBsAb and HBcAb), HCV (anti-HCV Ab) and HIV (anti HIV 1/2 Ab)
  - Cytokines (samples collected due to IRR)
- Urine parameters from
  - 24 hour urine
  - Spot urine
- Pregnancy tests (from serum and urine sample): B-hCG (only for female of childbearing potential)

Local laboratory parameters include

- Blood parameters from haematology
- Urine parameters from urinalysis, urine microscopy

### 11.6.2. Grading of laboratory results

Laboratory data grades of severity will be derived according to the Common Terminology Criteria for Adverse Events (CTCAE), version 5.0. A severity grade of 0 will be assigned when the value is within normal limits. Grade 5 will not be used.

Laboratory values having hyper or hypo shifts will be classified as a particular CTCAE grade irrespective of the shift direction (no differentiation between CTCAE grades due to increased, or decreased lab values).

Laboratory test results will also be flagged in listings by the low/normal/high classifications based on laboratory normal ranges.

For duplicate laboratory measurements with grades taken at the last assessment date on or before the start date of study treatment, the value of lower CTCAE grade will be considered as the baseline value.

For non-gradable laboratory values with duplicate measurements taken at the last assessment date on or before the start date of study treatment, the following rules apply:

- If both within normal range, use the average value
- If one within normal range and the other outside, use the one within normal range
- If both outside normal range, use the one closest to the normal range

Laboratory values with missing units or normal range may not be included in laboratory tables.

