**CCI**

Non-hematological TEAEs related to MOR202 reported in more than 5% of subjects overall in the FIH study were fatigue, infusion-related reactions, respiratory and urinary tract infections, diarrhea, nausea, hypokalemia, C-reactive protein increased, cough, constipation, hypophosphatemia, pyrexia, nasopharyngitis, and oral herpes.

Please refer to the Investigator Brochure for MOR202 for further details.

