#### Laboratory Tables

- Central haematology, coagulation and serum biochemistry parameters
  - Descriptive summaries of absolute values and absolute change from baseline values will be presented for continuous parameters for FAS by visit
  - Number (%) of subjects at each time point having clinical relevant findings of laboratory parameters will be tabulated by visit for each clinical laboratory parameter
  - For each laboratory parameter shifts in assessments from baseline (low, normal or high) to worst-post baseline will be presented based on classifications relative to the laboratory reference ranges (low/normal/high) for laboratory parameters where NCI-CTCAE grades are not defined. If a subject experiences both "low" and "high" assessments in the course of the trial, the worst post-baseline will be defined as "Low and High"
  - If NCI-CTCAE grades are available for a clinical laboratory parameter, frequency and shift tables based on grades will be created as follows:
    - Number (%) of subjects with worst post-baseline grade. Each subject will be counted only for the worst grade observed on-treatment.
    - Shift tables to compare baseline to the worst post-baseline value using CTCAE grades for laboratory parameters where grades are defined
- Central serology parameters
  - Descriptive summaries of absolute values and change from baseline values will be presented for FAS by visit
- Cytokine (due to IRR  $\geq$  grade 3)
  - Descriptive summaries of absolute values will be presented for FAS on visits where the IRR was observed (split by samples taken at time of IRR and 24 hours after IRR)
  - Absolute and relative change from baseline, if the baseline values are available
- 24 hour urine
  - Analysis of parameters from 24h urine is described in section 10.2
- Spot Urine
  - Descriptive summaries of absolute values and change from baseline values for UPCR from spot urine will be presented for FAS by visit

The tables will include only assessment on-treatment.

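### CTCAE laboratory grades ignore direction (SAP 11.6.2), so the graded laboratory tables can show a swing from low to high as no change or as improvement

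*SAP*

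**What the plan says.** SAP 11.6.2 derives laboratory severity grades from CTCAE version 5.0 and does not use grade 5. It states that "A severity grade of 0 will be assigned when the value is within normal limits", and that values with shifts in either direction are "classified as a particular CTCAE grade irrespective of the shift direction (no differentiation between CTCAE grades due to increased, or decreased lab values".

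SAP 11.6.3 (Laboratory Tables) plans two grade-based outputs for graded parameters. One is a worst post-baseline grade table, where "Each subject will be counted only for the worst grade observed on-treatment". The other is described as "Shift tables to compare baseline to the worst post-baseline value using CTCAE grades for laboratory parameters where grades are defined".

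A table that keeps direction is also planned, but it is "based on classifications relative to the laboratory reference ranges (low/normal/high) for laboratory parameters where NCI-CTCAE grades are not defined". That table includes a combined category for subjects who have both low and high values during the trial.

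Protocol 12.12.3 leaves the details of the laboratory analysis to the SAP.

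**The concern.** An analyte such as potassium can be abnormal on either side of normal, and the two sides are different disorders. If both share one grade scale, a table cell gives a severity but not the disorder. A shift table is meant to show how a subject changed under treatment, yet a move from one disorder to its opposite can appear there as stability or recovery.

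The SAP keeps direction for parameters without CTCAE grades and drops it for those that have them, and gives no reason for the difference.

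Safety is the primary objective, and the laboratory findings reported from the first-in-human study have a direction. Protocol 4.2.2 names lymphocytopenia, leukocytopenia, thrombocytopenia and anemia. Its list of MOR202-related events in more than 5% of subjects includes "diarrhea, nausea, hypokalemia, C-reactive protein increased, cough, constipation, hypophosphatemia". A reader will look to the graded tables for these patterns.

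**Working it through.** The plan states no figure on this point, so there is none to reproduce. The check applies the SAP's rules to every possible opposite-direction shift.

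**Inputs**
- Table scale: grades 0 to 4 (SAP 11.6.2; grade 0 is within normal limits, grade 5 is not used).
- Grade regardless of direction (SAP 11.6.2).
- One worst post-baseline grade per subject, cross-tabulated with the baseline grade (SAP 11.6.3).
- Analytes measured include potassium, sodium, calcium and magnesium (Protocol Table 3).
- Assumption: the analyte has grades 1 to 4 on both sides. The documents do not say which analytes do, although the rule itself presupposes that some are graded both ways. With fewer grades on one side there are fewer cells.

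**Step 1: count the cells.** Write a low grade as negative and a high grade as positive. Opposite-direction pairs of baseline and worst post-baseline value number 2 × 4 × 4 = 32. The planned table prints only the absolute grade.
- Equal grades, printed as no change: 2 × 4 = 8.
- Worst grade below baseline grade, printed as improvement: 2 × (3 + 2 + 1) = 12.
- Worst grade above baseline grade, printed as worsening with direction not shown: 2 × (1 + 2 + 3) = 12.
- Total: 8 + 12 + 12 = 32.

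**Step 2: compare with separate scales.** The examples suppose that the subject has no low value after baseline.

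| Baseline | Worst post-baseline | Planned table | Low scale | High scale |
|---|---|---|---|---|
| grade 1 low | grade 1 high | 1 to 1 | 1 to 0 | 0 to 1 |
| grade 2 low | grade 2 high | 2 to 2 | 2 to 0 | 0 to 2 |
| grade 2 low | grade 1 high | 2 to 1 | 2 to 0 | 0 to 1 |
| grade 1 low | grade 3 high | 1 to 3 | 1 to 0 | 0 to 3 |

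**Step 3: the case without a swing.** A subject who is normal at baseline and reaches grade 3 is printed as 0 to 3 whether the value was low or high. A row of the worst-grade table is therefore the sum of the low and high cases, and the two parts cannot be recovered from it. One subject moves a row by 1/20 = 5 percentage points in Cohort 1 and 1/10 = 10 points in Cohort 2.

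**Step 4: is direction supplied elsewhere in the laboratory tables?** The low/normal/high shift table excludes graded parameters. The by-visit table of clinically relevant findings specifies no direction. The by-visit summaries of change from baseline are signed, but they are group statistics in which opposite swings can cancel. No planned subject-level laboratory table therefore shows direction for an analyte graded both ways.

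**The case against.** The strongest reply is that direction is available in several other outputs.

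- **AE tables.** The first-in-human signals are adverse events, and the matching analysis here is TEAEs by preferred term and grade (SAP 11.1.4), where the term itself carries direction. Protocol 10.8.1 requires each abnormal laboratory finding to be judged for clinical relevance, and a relevant one is recorded as an AE.
- **AESIs.** Neutropenia and thrombocytopenia of grade 3 or higher are defined with a direction (Protocol 10.8.7) and have their own tables. Hematological AEs also get per-subject plots with grades (SAP 11.1.7).
- **Listings.** The out-of-range listing in SAP 11.6.3 gives the grade, below or above range, clinical relevance and significant worsening together. With about 30 subjects it can be read subject by subject.
- **Status.** The trial is descriptive, and laboratory shift tables are not an endpoint.

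Most of this stands and limits the harm. Two things remain. The AE route depends on investigator judgment, and the graded tables are the summary that does not. The listings hold the information, but the reader would have to count incidence by direction by hand.

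A reader might infer that the trial could not confirm or exclude hypokalemia or the cytopenias seen earlier. The documents do not support that, because the AE, AESI and listing routes keep direction. Nor do they support a count of affected analytes or an expected number of misread subjects: neither document lists the analytes graded both ways or gives frequencies. An argument that background therapies push potassium in opposite directions would rest on outside knowledge, and the documents give no figure for diuretic use.

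**Conclusion.** The point holds for the graded laboratory tables only. As planned, the worst-grade and baseline-to-worst shift tables do not show which disorder occurred for analytes graded in both directions. Of the 32 opposite-direction cells, 20 (8 + 12) read as no change or improvement. How many subjects would fall in those cells cannot be derived from the documents. No data are lost, and neither the TEAE analysis nor any endpoint estimate changes.

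The conclusion rests on one assumption, that some measured analytes have CTCAE grades on both sides, which the wording of SAP 11.6.2 itself presupposes. The change is worth making because a stated rule produces a misleading table in a trial whose primary objective is safety, and correcting it is cheap.

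**What to change.** 1. In SAP 11.6.2, replace the direction-blind sentence: analytes with CTCAE grades in both directions are graded on two separate scales, one low and one high.
2. Reword the grade 0 rule for these scales to mean not abnormal in that direction. Otherwise a high value set to grade 0 on the low scale would contradict the present rule that grade 0 means within normal limits.
3. Keep the duplicate-baseline rule workable: choose one value per analyte first, then grade that value on both scales.
4. In SAP 11.6.3, produce the worst-grade and shift tables per direction for these analytes, and list the analytes concerned.

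At minimum, extend the existing low/normal/high shift table, with its combined low-and-high category, to graded parameters. This would show direction but not severity by direction.

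Cost: SAP wording, some programming and slightly longer tables. No new data are needed.

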### 11.6.3. Laboratory analysis

Laboratory data that are continuous in nature but are less than the lower limit of quantitation or above the upper limit of quantitation will be imputed. The limit of quantitation will be used for calculation of descriptive statistics if the data is reported in the form of " $\leq x$ " or " $< x$ " or " $\geq x$ " or " $> x$ " (x is considered as the limit of quantitation).

The following analysis on laboratory parameters by cohort and overall on FAS will be performed:

#### Laboratory Tables

- Central haematology, coagulation and serum biochemistry parameters
  - Descriptive summaries of absolute values and absolute change from baseline values will be presented for continuous parameters for FAS by visit
  - Number (%) of subjects at each time point having clinical relevant findings of laboratory parameters will be tabulated by visit for each clinical laboratory parameter
  - For each laboratory parameter shifts in assessments from baseline (low, normal or high) to worst-post baseline will be presented based on classifications relative to the laboratory reference ranges (low/normal/high) for laboratory parameters where NCI-CTCAE grades are not defined. If a subject experiences both "low" and "high" assessments in the course of the trial, the worst post-baseline will be defined as "Low and High"
  - If NCI-CTCAE grades are available for a clinical laboratory parameter, frequency and shift tables based on grades will be created as follows:
    - Number (%) of subjects with worst post-baseline grade. Each subject will be counted only for the worst grade observed on-treatment.
    - Shift tables to compare baseline to the worst post-baseline value using CTCAE grades for laboratory parameters where grades are defined
- Central serology parameters
  - Descriptive summaries of absolute values and change from baseline values will be presented for FAS by visit
- Cytokine (due to IRR  $\geq$  grade 3)
  - Descriptive summaries of absolute values will be presented for FAS on visits where the IRR was observed (split by samples taken at time of IRR and 24 hours after IRR)
  - Absolute and relative change from baseline, if the baseline values are available
- 24 hour urine
  - Analysis of parameters from 24h urine is described in section 10.2
- Spot Urine
  - Descriptive summaries of absolute values and change from baseline values for UPCR from spot urine will be presented for FAS by visit

The tables will include only assessment on-treatment.

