### 8.7. Treatment management of subjects with toxicity

For the first dosing of MOR202, subjects should exhibit hemoglobin, leucocyte, neutrophil and platelet counts meeting the eligibility criteria. They should not have an active infection  $\geq$  grade 2.

For subsequent doses, in case a subject shows laboratory values as listed below, further treatment of the subject has to be interrupted:

- Hemoglobin level < 60 g/L (grade 3): interruption until resolved to  $\geq 80$  g/L.
- Platelet count <  $75.0 \times 10^9/L$  (grade 2): interruption until resolved to  $\geq 100.0 \times 10^9/L$ .
- Neutrophil count <  $1.000 \times 10^9/L$  (grade 3): interruption until resolved to  $\geq 1.500 \times 10^9/L$ .

If the subject exhibits any other clinically relevant adverse drug reaction  $\geq$  grade 3, MOR202 administration has to be interrupted until the toxicity has resolved to grade 2 or better.

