## **8.8. Subject Discontinuation of IMP and Subject Withdrawal**

### **8.8.1. Discontinuation due to toxicity**

MOR202 treatment must be permanently discontinued, if:

- Needing platelet transfusion.
- Not recovering to  $\leq$  grade 2 from  $\geq$  grade 3 ADRs related to MOR202 within 21 days despite adequate treatment of the ADR.
- Experiencing grade 4 IRR.

Subjects discontinuing MOR202 treatment will have their EOT visit (earliest after 28 days after last dose of MOR202) and enter the follow-up phase.

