## 10.8. Safety Assessments

Safety monitoring for all subjects enrolled will include laboratory safety assessments (e.g., hematology, serum biochemistry, urinalysis and coagulation) and clinical evaluations (e.g., physical examinations, vital signs, 12-lead ECG) as detailed in the Schedule of Assessments ([Table 2](#)).

Laboratory and AE toxicities will be graded according to NCI-CTCAE, version 5.0. Subjects who experience any toxicity should be followed until the toxicity has stabilized, the toxicity has returned to the baseline level, or a new treatment has commenced.

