		Section 7.10 The 'Assessment windows and analysis visits' section was substituted by 'Analysis visits' section. Assessment windows are disregarded in current version and the main difference in analysis windows approach is that:  nominal (actual) visit dates will be used as per eCRF,  unscheduled visits for visit-based analyses will be disregarded, except baseline assessment  unscheduled visits will be considered only for patient data listings and spaghetti plots	Applying the assessment windows clarifies the approach for using unscheduled visit data.
		Section 9.6.1 Categories of exposure duration and the cumulative exposure duration were defined based on study days	This approach enables an easier interpretation of the results
		Section 10.2 Spaghetti plots for % change from baseline for each subject were added	These plots will allow detailed exploration of the results

Version	Date	Changes	Rationale for Change
		All plots will be produced also for Urine creatinine parameter	
		Section 10.3 Analysis of Proteinuria response will be evaluated also on PPS population	UPCR is an important efficacy endpoint and the analyses done on PPS population will allow detailed interpretation of the results
		Section 10.4 Analysis of Renal Function assessed by eGFR will be evaluated also on PPS population	Renal Function is an important efficacy endpoint and the analyses done on PPS population will allow detailed interpretation of the results
		Section 10.4 The eGFR will be evaluated as % change from baseline to each visit until End of Study.	No sense from clinical point of view doing the evaluation from EOT until EOS
		Section 10.5 The serum albumin levels will be evaluated as % change from baseline to each visit until End of Study.	No sense from clinical point of view doing the evaluation from EOT until EOS
		Section 10.7 Number (%) of subjects with doubling of serum creatinine either vs. baseline or any nadir measured during the trial was removed from the analyses	Is not needed per Protocol
		Section 10.8 The kidney specific subscales will be derived using additional SAS code (Appendix 1).	The evaluation of kidney specific subscales is not included in core scoring software provided by Optum
		Section 10.9 The kinetics of anti-PLA2R titers will be evaluated as % change from baseline to each visit until End of Study.	No sense from clinical point of view doing the evaluation from EOT until EOS

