## 7.8. On treatment assessment/event

### On-treatment assessment/event

An on-treatment assessment/event is defined as any assessment/event happening after the start date of study treatment, i.e. assessments/events happening in the following time interval (including the lower and upper limits):

[Start date of study drug +1 day; End date of study drug + 28 days].

Assessments collected post-dose on the start date of study drug are also considered as on-treatment assessments. Data listings will include all assessments/events, flagging those which are not on-treatment assessments/events.

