## 7.10. Analysis visits

For parameters that will be summarized by visit, the nominal visit as recorded in the eCRF (i.e. actual visit date) will be used (disregarding the allowed assessment windows). Data collected in unscheduled visits will be displayed in patient data listings and spaghetti plots only, except Baseline assessment (refer to section 7.7). The unscheduled visit results will be flagged in the listings accordingly and will be highlighted by asterisks on spaghetti plots.

In the case of multiple records for one visit, selection rules are described in section 7.11 (below).

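### SAP 7.10, taken literally, keeps unscheduled central results out of the worst-grade and shift tables of SAP 11.6.3; the intended reach is arguable and two sentences would settle it

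*SAP*

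**What the plan says.** SAP 11.6.3 (Laboratory Tables) places the CTCAE frequency and shift tables under "Central haematology, coagulation and serum biochemistry parameters". For the worst post-baseline grade it says: "Each subject will be counted only for the worst grade observed on-treatment". The shift tables compare baseline with the worst post-baseline value. The subsection closes by limiting its tables to on-treatment assessments. It does not say whether unscheduled results count.

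SAP 7.8 defines the on-treatment interval as "Start date of study drug +1 day; End date of study drug + 28 days" and covers any assessment within it.

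SAP 7.10 opens with parameters that are summarized by visit, for which the nominal eCRF visit is used. It then says: "Data collected in unscheduled visits will be displayed in patient data listings and spaghetti plots only, except Baseline assessment". The SAP Document History entry for this rule (version 5.0) describes it as disregarding unscheduled visits in visit-based analyses, and adds that "unscheduled visits will be considered only for patient data listings and spaghetti plots".

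**The concern.** A worst-grade table is neither a listing nor a spaghetti plot. If 7.10 is applied as written, a low count seen only at an unscheduled central draw cannot enter a table that claims to show the worst on-treatment grade.

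Such draws are plausible. Protocol 10.8 says: "Subjects who experience any toxicity should be followed until the toxicity has stabilized, the toxicity has returned to the baseline level". Protocol 8.7 adds that, for hemoglobin, platelets and neutrophils, "in case a subject shows laboratory values as listed below, further treatment of the subject has to be interrupted", and dosing resumes only on recovery. The schedule of assessments has no row for interim rechecks.

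Cytopenias are the leading known harm of MOR202 (Protocol 4.2.2 and 6.8). An abnormal laboratory value becomes an AE only if the investigator judges it clinically relevant (Protocol 10.8.1). Leukocyte and lymphocyte counts have no listed hold threshold in 8.7 and are not AESIs in 10.8.7. For these, the graded laboratory table is the main summary that does not depend on that judgement. At stake is whether it understates the worst grade for some subjects.

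**Working it through.** **Plan figures.** The plan gives no figure on this point. Its design probabilities (Protocol 12.5) reproduce, 1 − 0.90^20 = 0.878 (stated 88%) and 1 − 0.85^10 = 0.803 (stated 80%), but they concern the occurrence of AEs and do not enter here.

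**The texts side by side.**

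1. SAP 7.10 confines unscheduled data to two kinds of output and makes one exception, baseline. Worst-value tables are not excepted.
2. Its opening scope is parameters summarized by visit. SAP 11.6.3 summarizes central haematology by visit, so the parameter falls within that scope. If the scope is read as the type of table instead, a worst-value table falls outside it.
3. SAP 7.8 and 11.6.3 point towards including everything in the interval, but neither mentions unscheduled results or sets 7.10 aside.
4. SAP 7.11 separates analyses that need one value per visit from those that do not. It gives no rule for unscheduled results.
5. SAP 10.10 expressly admits unscheduled visits, but only for the sensitivity analysis of named efficacy endpoints. Laboratory safety has no matching sentence.

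The text therefore supports two programs: one that drops unscheduled central results from the worst grade and one that keeps them.

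**Where a result could drop out.** The schedule of assessments (Protocol Table 2) plans central CBCs before dosing at C1D8, C1D15, C1D22, C2D1, C3D1, C4D1, C5D1 and C6D1: 8 post-baseline samples in a full course, 7 days apart up to Day 29 and 28 days apart afterwards. The EOT sample (planned Day 169) also counts if it falls within the on-treatment interval. An interim central draw is exposed to the 7.10 rule. So is one after permanent discontinuation, because Protocol 8.8.1 says "Subjects discontinuing MOR202 treatment will have their EOT visit (earliest after 28 days after last dose of MOR202"; an on-treatment count before that visit has no scheduled slot.

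**Size per affected subject.** With the planned cohort sizes (Protocol 12.5), one subject changes a worst-grade percentage by:

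- Cohort 1: 1/20 = 5.0 points
- Cohort 2: 1/10 = 10.0 points
- Overall: 1/(20 + 10) = 1/30 = 3.3 points

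This applies only if none of that subject's scheduled on-treatment central samples reaches the same grade. For example, if a Cohort 1 subject's scheduled samples reach grade 2 and one unscheduled central sample reaches grade 3, the literal rule counts the subject at grade 2. Including the sample lowers the grade 2 percentage by 5 points and raises the grade 3 percentage by 5 points.

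**The case against.** The strongest reply is that 7.10 was never meant to reach these tables. It opens with by-visit parameters, the change log speaks of visit-based analyses, and a worst-grade table is not by-visit. The more specific wording in 11.6.3, with the any-assessment definition in 7.8, would then prevail. This reading is reasonable and may well be the intended one. It does not remove the conflict with the word limiting unscheduled data to listings and plots, which no section overrides.

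Two further replies stand and limit the size. First, Protocol 10 allows visits to be postponed for toxicity, and SAP 7.10 keeps the nominal visit regardless of windows. A CBC at a postponed dosing visit therefore remains a scheduled result; only additional draws are exposed. Second, other outputs carry much of the information. Grade 3 or higher neutropenia and thrombocytopenia are AESIs (Protocol 10.8.7), dose interruptions are tabulated (SAP 9.6.3), haematological TEAEs are plotted by subject (SAP 11.1.7), and the laboratory listings keep the value.

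A reader might also infer that leaving out local CBCs is a defect. The documents do not support that: Protocol 12.12.3 specifies central parameters, SAP 11.6.3 follows it, and every scheduled dosing visit has a central CBC alongside the local one. A local-haematology table would be a preference. Nor is an EOT sample taken after day 28 part of this point: it leaves the tables through the SAP 7.8 cut-off, not the rule on unscheduled visits.

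**Conclusion.** The point holds as a minor inconsistency. Read literally, SAP 7.10 excludes unscheduled on-treatment central results from the worst-grade and shift tables, which contradicts what SAP 11.6.3 says those tables show. Whether this was intended is arguable, so it should not be read as an established loss of low counts.

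The number of affected subjects is unknown and may be zero. The documents do not say how many interim draws to expect, or whether rechecks go to the central laboratory. The figures of 5, 10 and 3.3 points are effects per subject at the planned cohort sizes, not estimates of the total effect.

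A reader might infer that the safety conclusion as a whole is compromised. It is not: the primary endpoint rests on TEAEs, and the AE and AESI tables and the listings do not use the worst-grade derivation.

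**What to change.** In SAP 7.10, add: *The exclusion of unscheduled results applies to by-visit summaries only.*

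In SAP 11.6.3, add: *Worst post-baseline grade and baseline-to-worst shift tables use all on-treatment central results, scheduled and unscheduled.* Label these tables as central laboratory.

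The cost is two sentences and a label, with a matching line in the analysis dataset specifications. No new data are needed, and sample size and by-visit summaries do not change. The one downside for the sponsor is that the cytopenia grades may look slightly less favourable.
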